4.1.2 Preclinical and Clinical Trial Data

Refer to the Investigator's Brochure for Preclinical and Clinical data.

4.2 Rationale

Current RADVAX™ trial at Penn using hypofractionated RT and ipilimumab

Simulated by our own anecdotal report of a patient having progressive disease on immunomodulatory therapy who had a dramatic abscopal response to radiotherapy, we initiated a phase I/II trial at Penn to determine whether it would be safe to deliver ipilimumab following hypofractionated radiotherapy. Patients received either 2 or 3 fractions of radiotherapy, followed by 4 cycles of the anti-CTLA4 agent ipilimumab. By trial design patients were required to have at least two discrete metastatic lesions from melanoma, only one of which was irradiated.

The primary goal of the trial was to assess safety. To date 21 patients have been enrolled. Overall treatment was well tolerated with no deaths attributable to therapy and no grade 4 toxicities. The most common grade 3 toxicity was anemia. There were no dose-limiting toxicities (DLTs), which for this study was defined as any grade 4 or higher immune treatment-related toxicity or grade 3 or higher non-immune treatment (RT-related) toxicity. Fourteen patients completed the entire 4 cycles of ipilimumab (2 patients completed only 2 cycles and 2 patients only 3 cycles due to progressive disease; 2 patients received only 3 cycles due to the development of colitis).

The impact of the therapy on the irradiated lesion and the non-irradiated lesion(s) was evaluated using two standard modalities: (i) ¹⁸F-2-deoxyfluoro-2-deoxyglucose (FDG) activity on positron emission tomography-computer tomography (PET-CT) as a measure of biological effects of therapy and (ii) CT imaging for Response Evaluation Criteria in Solid Tumors (RECIST 1.1) assessment. 19 patients have been followed long enough to evaluate radiologic response. Metabolic responses were observed by FDG-PET-CT in the irradiated (“index”) lesion in 9 out of 19 patients (47%) with 4 of these 9 patient showing a complete metabolic response (CMR) and 5 of the 9 showing a partial metabolic response (PMR). Of the remaining 10 patients, 7 did not have repeat PET imaging, and 3 had stable metabolic disease (SMD). For the lesions that were not irradiated, metabolic responses were seen in 4 patients (21%), of which 2 were CMR and 2 were PMR. Of the remaining 15 patients, 7 did not have repeat PET imaging, and 8 had progressive metabolic disease (PMD). Using RECIST criteria on non-irradiated lesions, 4 out of 19 patients (21%) had a partial response (PR), 2 patients had stable disease (SD), and 12 patients had progressive disease (PD). One patient did not have CT scanning performed to assess tumor response.

The median progression-free survival (PFS) is 4.9 months and the median overall survival (OS) 10.7 months. Ipilimumab alone resulted in a response rate of 10.9% in the study by Hodi *et al.* (6). In summary, the combination of ipilimumab with hypofractionated radiotherapy was safe without DLTs. However, ipilimumab-related side effects were significant and the combination of ipilimumab and RT showed modest improvement over what is reported in the literature. Although our study was not designed to assess response, the results do not show that the majority of the patients have significant shrinkage of their unirradiated lesions in response to radiation. The results of our Phase I study support the investigation of the anti-PD1 agent, Pembrolizumab, with radiation given its probable

superior toxicity profile compared to ipilimumab.

Preclinical Studies of RT and anti-PD1/PD-L1 therapy

RT has also been combined with inhibition of the PD1/PD-L1 pathway. *Deng et al.* found that PD-L1 was upregulated in the tumor microenvironment after radiation (16). Administration of anti-PD-L1 antibody enhanced the efficacy of RT through a cytotoxic T cell-dependent mechanism. Concomitant with tumor regression, RT and anti-PD-L1 synergistically reduced the local accumulation of tumor-infiltrating myeloid-derived suppressor cells (MDSCs), which suppress T cells and alter the tumor immune microenvironment.

Our own group at Penn has generated data using anti-PD1 therapy with RT. As noted above, emerging data indicate that optimal results will require combination therapies, of which radiation (RT) may hold promise. The effectiveness and mechanisms of action for this combination have not been well characterized, which potentially hinders efficient clinical translation. To address these issues, we have developed several pre-clinical mouse models for melanoma, breast cancer, and other cancer types to mechanistically dissect the combination of RT and immune checkpoint blockade. Using these models, we have determined that RT and immune checkpoint inhibitors such as anti-PD-1/PD-L1 cooperate to promote tumor response in both irradiated and unirradiated tumors ([name] personal communication). Survival and complete responses are significantly improved, and long-term anti-tumor immunity ensues. Using a series treatment resistant sublines that we derived combined with unbiased genome-wide and immune approaches, we have discovered mechanisms of resistance and druggable targets to inhibit resistance. Studies on immune mechanisms and biological effects of RT are providing insight into how combination therapy can work in non-redundant ways to improve response. Insight into immune mechanisms has also driven the discovery of potential blood-based biomarkers for response. In summary, by using pre-clinical models, our preclinical studies demonstrate that anti-PD1 therapy in combination with hypofractionated radiotherapy leads to significant responses in non-index (non-irradiated) lesions and therefore supports the proposed trial of Pembrolizumab with radiation. We plan to continue to address critical questions on which combinations are effective, what mechanisms of resistance might emerge, how resistance can be rationally targeted, and whether mechanistic insight can guide the development of biomarkers to predict response.

4.2.1 Rationale for the Trial and Selected Subject Population

Anti-PD1 therapies have shown activity in melanoma and NSCLC (XX-ref). It is not clear if these agents will have activity in other diseases nor is it clear whether the immunostimulatory effect of hypofractionated radiotherapy in combination with these agents is cancer-specific or dependent upon single agent activity of the immunotherapeutic agent. Our preclinical data suggest that activity is observed in a broader range of tumor types. Therefore, we propose to study the safety and preliminary efficacy of the combination of Pembrolizumab and radiotherapy in five groups of patient diagnoses: melanoma, NSCLC, pancreatic cancer, breast cancer, and other. Our hypothesis is that safety will be established and that an exploratory analysis will demonstrate robust responses in all disease groups.

4.2.2 Rationale for Dose Selection/Regimen/Modification

An open-label Phase I trial (Protocol 001) is being conducted to evaluate the safety and clinical activity of single agent PEMBROLIZUMAB. The dose escalation portion of this trial evaluated three dose levels, 1 mg/kg, 3 mg/kg, and 10 mg/kg, administered every 2 weeks (Q2W) in subjects with advanced solid tumors. All three dose levels were well tolerated and no dose-limiting toxicities were observed. This first in human study of PEMBROLIZUMAB showed evidence of target engagement and objective evidence of tumor size reduction at all dose levels (1 mg/kg, 3 mg/kg and 10 mg/kg Q2W). No MTD has been identified to date. 10.0 mg/kg Q2W, the highest dose tested in PN001, will be the dose and schedule utilized in combination with hypofractionated radiotherapy. Recent data from other clinical studies within the PEMBROLIZUMAB program has shown that a lower dose of PEMBROLIZUMAB and a less frequent schedule may be sufficient for target engagement and clinical activity.

PK data analysis of PEMBROLIZUMAB administered Q2W and Q3W showed slow systemic clearance, limited volume of distribution, and a long half-life (refer to IB). Pharmacodynamic data (IL-2 release assay) suggested that peripheral target engagement is durable (>21 days). This early PK and pharmacodynamic data provides scientific rationale for testing a Q2W and Q3W dosing schedule.

A population pharmacokinetic analysis has been performed using serum concentration time data from 476 patients. Within the resulting population PK model, clearance and volume parameters of PEMBROLIZUMAB were found to be dependent on body weight. The relationship between clearance and body weight, with an allometric exponent of 0.59, is within the range observed for other antibodies and would support both body weight normalized dosing or a fixed dose across all body weights. PEMBROLIZUMAB has been found to have a wide therapeutic range based on the melanoma indication. The differences in exposure for a 200 mg fixed dose regimen relative to a 2 mg/kg Q3W body weight based regimen are anticipated to remain well within the established exposure margins of 0.5 – 5.0 for PEMBROLIZUMAB in the melanoma indication. The exposure margins are based on the notion of similar efficacy and safety in melanoma at 10 mg/kg Q3W vs. the proposed dose regimen of 2 mg/kg Q3W (i.e. 5-fold higher dose and exposure). The population PK evaluation revealed that there was no significant impact of tumor burden on exposure. In addition, exposure was similar between the NSCLC and melanoma indications. Therefore, there are no anticipated changes in exposure between different indication settings.

4.2.3 Rationale for Primary Endpoint

This is a Phase I study that will determine the safety of combining Pembrolizumab with hypofractionated radiotherapy. The absence of clinical data regarding the safety of this combination mandates the performance of a Phase I trial. The primary endpoint, therefore, will be the safe dose or doses of hypofractionated radiotherapy in combination with Pembrolizumab as defined by 0 or 1 DLTs observed in 6 patients within each radiation dose cohort.

4.2.3.1 Efficacy Endpoints

This is a Phase I study and therefore, efficacy will not be the primary endpoint. Nonetheless, we have designed the study to obtain an estimate of the immune-related response rate in non-index metastatic lesions of the combination of Pembrolizumab and hypofractionated radiotherapy (please see statistical section for greater detail).

4.2.3.2 Biomarker Research

While this is a Phase I study and not necessarily powered for extensive statistical evaluation of biomarkers, we will begin to directly test whether promising biomarkers exist for more in depth analysis. The focus on immune-related response rate in non-index metastatic lesions will be the basis for examining circulating immune responses for correlates of tumor response.

The main goals of these studies are to perform in-depth immune phenotyping and analysis of samples from humans treated with hypofractionated radiotherapy in combination with Pembrolizumab. Biosamples (blood and, where available, tumor) obtained from patients before and at serial time points during treatment will be analyzed. The primary goals for the basic studies with these human samples will be:

- High dimensional (15-17 color) flow cytometry to analyze T cell subsets (including naïve, effector, memory (effector memory and central memory), effector memory RA, exhausted, Th1, Treg and Tf_h), co-expression of sets of multiple inhibitory receptors by relevant T cell subsets, transcription factor expression, and T comprehensive functional analysis (expression of cytokines, chemokines, cytotoxic molecules, and degranulation). These studies will focus on sophisticated immune phenotyping and defining correlates of response to hypofractionated radiotherapy in combination with Pembrolizumab. These studies will be performed on PBMC and, where available, TIL.
- Deep sequencing of the TCR will also be performed from blood and tumor as a novel way to interrogate tumor-specific T-cell responses induced by treatment. This method does not require a priori understanding of a particular tumor antigen or MHC. Of particular interest will be evidence of TCR clones increasing in the circulation after therapy that are also found in the patient's tumor. Such observations would be consistent with a “vaccine effect” of therapy and the persistence of these T cell clones over time may be a predictor of a durable response.
- Whole genome transcriptional profiling will be performed using PBMC and/or tumor to develop predictors of responses and to reveal underlying pathways. These studies will be integrated with findings from pre-clinical models to help define novel signatures of clinical responses.

Summary

Based on our own clinical data with RT and ipilimumab, and pre-clinical data from our group and in the literature, we propose a stratified phase I clinical trial of hypofractionated radiotherapy to an isolated index lesion in combination with the PD-1 inhibitor, Pembrolizumab in patients with metastatic cancers who have failed anti-PD-1 therapy (melanoma and NSCLC) and patients with metastatic cancers who have progressed after at least one regimen of systemic therapy (breast, pancreas, and other). In our protocol, the primary goal is to demonstrate that Pembrolizumab can be safely administered with hypofractionated radiotherapy. We will also estimate the immune-related response rate of non-index metastatic lesions.

5.0 METHODOLOGY

5.1 Entry Criteria

5.1.1 Diagnosis/Condition for Entry into the Trial

This is a cohort study of a fixed dose of Pembrolizumab in combination with two distinct regimens of hypofractionated radiotherapy. There will be five groups of patient diagnoses:

- Metastatic melanoma patients who have progressed while on PD-1 or PDL-1 therapy or have been on such therapy for at least 6 months with recent scan showing stable disease
- Metastatic NSCLC patients who have progressed while on PD-1 or PDL-1 therapy or have been on such therapy for at least 6 months with recent scan showing stable disease
- Metastatic & locally advanced pancreatic cancer patients
- Metastatic Breast cancer patients
- Other metastatic cancer patients

5.1.2 Subject Inclusion Criteria

In order to be eligible for participation in this trial, the subject must:

1. Be willing and able to provide written informed consent/assent for the trial.
2. Be ≥ 18 years of age on day of signing informed consent.
3. Histologically confirmed diagnosis of cancer as per the cohort specifications
4. Stage IV cancer by AJCC staging criteria (except for pancreatic cancer cohort)
5. Locally advanced or metastatic pancreatic cancer for the pancreatic cancer cohort

6. Progression of disease while on anti-PD-1 or anti-PD-L1 therapy for melanoma and NSCLC patients. For this group, patients must meet the following criteria:
 - a. Received at least 2 doses of an anti-PD1 or anti-PD-L1 therapy
 - b. Had progressive disease documented radiologically by RECIST v1.1 criteria.
7. Patients with metastatic melanoma or NSCLC who have been on anti-PD1 or anti-PD-L1 therapy for at least 6 months with a recent scan showing stable disease are also eligible.
8. Progression or refractory disease to at least one regimen of therapy for metastatic disease in the breast and pancreatic cancer cohorts
9. Presence of an index lesion ≥ 1 cm amenable to hypofractionated radiotherapy
10. Patients who have metastatic cancer must have at least one lesion that is outside the radiation field that measures greater than one cm that can be followed by RECIST 1.1. This lesion, if it is close to the radiated lesion, must receive no more than 10% of the dose prescribed to the target lesion.
11. Have provided tissue from an archival tissue sample or newly obtained core or excisional biopsy of a tumor lesion.
12. Have a performance status of 0 or 1 on the ECOG Performance Scale.
13. Ability to tolerate hypofractionated radiation therapy (e.g. lie flat and hold position)
14. Demonstrate adequate organ function as defined in Table 1, all screening labs should be performed within 21 days of signing study consent.

Table 1 Adequate Organ Function Laboratory Values

System	Laboratory Value
Hematological	
Absolute neutrophil count (ANC)	$\geq 1,500 / \mu\text{L}$
Platelets	$\geq 100,000 / \mu\text{L}$
Hemoglobin	$\geq 9 \text{ g/dL}$ or $\geq 5.6 \text{ mmol/L}$
Renal	
Serum creatinine OR Measured or calculated ^a creatinine clearance (GFR can also be used in place of creatinine or CrCl)	$\leq 1.5 \times$ upper limit of normal (ULN) OR $\geq 60 \text{ mL/min}$ for subject with creatinine levels $> 1.5 \times$ institutional ULN
Hepatic	

Serum total bilirubin	$\leq 1.5 \times \text{ULN}$ OR
	Direct bilirubin $\leq \text{ULN}$ for subjects with total bilirubin levels $> 1.5 \text{ ULN}$
AST (SGOT) and ALT (SGPT)	$\leq 2.5 \times \text{ULN}$ OR $\leq 5 \times \text{ULN}$ for subjects with liver metastases

^aCreatinine clearance should be calculated per institutional standard.

15. Female subject of childbearing potential should have a negative urine or serum pregnancy within 72 hours prior to receiving the first dose of study medication. If the urine test is positive or cannot be confirmed as negative, a serum pregnancy test will be required.

16. Female subjects of childbearing potential should be willing to use 2 methods of birth control or be surgically sterile, or abstain from heterosexual activity for the course of the study through 120 days after the last dose of study medication (Reference Section 5.7.2). Subjects of childbearing potential are those who have not been surgically sterilized or have not been free from menses for > 1 year.

16. Male subjects should agree to use an adequate method of contraception starting with the first dose of study therapy through 120 days after the last dose of study therapy.

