7.1.4.4.2 Tumor Response

To systematically characterize additional patterns of response in patients with metastatic cancer, Response Evaluation Criteria in Solid Tumors (RECIST) version 1.1 will be used. The details as to how RECIST criteria are applied are given below.

A maximum of 5 target lesions in total (and up to 2 per organ) can be identified at baseline and measured throughout the course of therapy. In order to be considered a measurable target lesion, a nodal lesion must be ≥ 1.5 cm in short axis diameter (SAD), and an extranodal lesion must be ≥ 1.0 cm in longest diameter (LD). The irradiated lesion will not be included as a target lesion for measurement using RECIST. The sum of diameters of the target lesions (SAD for nodal lesions and LD for extranodal lesions) is followed through the course of therapy.

Disappearance of all known lesions will be counted as complete response (CR). A reduction of at least 30% in the sum of the diameters of target lesions is defined as partial response (PR). Progressive disease (PD) is defined as $\geq 20\%$ increase in the sum of diameters of target lesions from nadir (including baseline if it is smallest sum). PD is also defined as unequivocal progression of existing non-target lesions that merits discontinuation of therapy.

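### Entry criterion 10 does not clearly require a target lesion: a metastatic patient whose only non-irradiated disease is a node over 1 cm but under 1.5 cm short axis could enrol and could not be scored PR

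*Combined protocol and SAP*

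**What the plan says.** Criterion 10 in Section 5.1.2 asks that a metastatic patient have "at least one lesion that is outside the radiation field that measures greater than one cm that can be followed by RECIST 1.1". A second sentence limits the dose which that lesion may receive to 10% of the index prescription. The criterion does not say which diameter is measured, does not separate nodes from other lesions, and does not refer to target lesions or to Section 7.1.4.4.2.

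Section 7.1.4.4.2 (Tumor Response) sets two limits for a target lesion: "an extranodal lesion must be ≥ 1.0 cm in longest diameter (LD"), and "a nodal lesion must be ≥ 1.5 cm in short axis diameter (SAD"). It adds: "The irradiated lesion will not be included as a target lesion for measurement using RECIST". The response categories follow:

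- PR: "A reduction of at least 30% in the sum of the diameters of target lesions is defined as partial response (PR").
- CR: "Disappearance of all known lesions will be counted as complete response (CR").
- PD: a rise of at least 20% in the target sum from nadir, or unequivocal worsening of non-target disease.

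Section 8.0 illustrates response rates on all 38 patients in Cohort 1 and all 32 in Cohort 2. It then makes zero-response statements by disease: 0/14 and 0/20 for melanoma and NSCLC, 0/6 and 0/10 for pancreas, breast and other cancers. No response-evaluable set is defined. Section 5.8 replaces patients who do not complete therapy, not patients who lack a target lesion.

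**The concern.** The entry rule and the scoring rule use different size limits for nodes. A node that meets the entry size can be too small to be a target. If it is the patient's only disease outside the radiation field, there is no target sum, and neither PR nor target-based PD can be calculated.

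Response in non-index lesions is the secondary objective (Section 3.2), and Section 4.2.3.1 says the study was designed to estimate it. Patients who stay in the denominator but cannot be scored PR would pull the estimated rate down. They would also thin the information behind the zero-response statements, which have little margin.

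**Working it through.** **Step 1: compare the two rules by lesion type.**

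| Only non-irradiated lesion | Entry size (criterion 10) | Target lesion (7.1.4.4.2) | PR can be scored |
|---|---|---|---|
| Extranodal, over 1 cm longest diameter | met | yes (≥ 1.0 cm) | yes |
| Node, ≥ 1.5 cm short axis | met | yes | yes |
| Node, over 1 cm but under 1.5 cm short axis | met | no | no |

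The extranodal limits agree, provided the entry size is the longest diameter. Only the third row is a gap. The index lesion cannot fill it because it is excluded as a target. CR needs no target sum and non-target PD needs none, so both remain open to this patient.

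**Step 2: reproduce the plan's zero-response figures.** If the true rate is p, the chance of no responses in n patients is (1 − p)^n. The one-sided 95% upper bound at zero responses is 1 − 0.05^(1/n).

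| Statement in Section 8.0 | (1 − p)^n | Upper bound |
|---|---|---|
| 0/14 rules out 20% | 0.80^14 = 0.044 | 19.3% |
| 0/20 rules out 15% | 0.85^20 = 0.0388 | 13.9% |
| 0/6 rules out 40% | 0.60^6 = 0.0467 | 39.3% |
| 0/10 rules out 27% | 0.73^10 = 0.043 | 25.9% |

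All four hold as one-sided statements. Two-sided bounds (23.2%, 16.8%, 45.9%, 30.8%) would not support them, so one-sided is taken as the plan's intention. The ten exact intervals in Table 14 also reproduce to the printed decimal.

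**Step 3: remove m unscorable patients from a group.** The documents give no count, so m is an assumption. The bound becomes 1 − 0.05^(1/(n − m)).

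| Group | Stated | m = 1 | m = 2 |
|---|---|---|---|
| n = 14 | 20% | 0/13: 20.6% | 0/12: 22.1% |
| n = 20 | 15% | 0/19: 14.6% | 0/18: 15.3% |
| n = 6 | 40% | 0/5: 45.1% | 0/4: 52.7% |
| n = 10 | 27% | 0/9: 28.3% | 0/8: 31.2% |

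One such patient in the group is enough to lose the 20%, 40% and 27% statements. The 15% statement survives one and is narrowly lost with two. A patient from the safety phase affects only the pooled statements (n = 20 or 10).

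**Step 4: keep them in the denominator as non-responders instead.** Assume a 25% rate among scorable patients and no CR among the others. In Cohort 1, two such patients give 25% × 36/38 = 23.7% and four give 25% × 34/38 = 22.4%. In Cohort 2, two give 25% × 30/32 = 23.4%.

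**The case against.** The strongest reply is that criterion 10 already requires a lesion that RECIST 1.1 can follow. Section 7.1.4.4.2 speaks of following only in connection with the target sum. On that reading a small node does not qualify and there is no gap. This has real force. A reader might infer that the plan admits any lesion over 1 cm, and the documents do not support that: the RECIST qualifier is there and may well have been meant as restrictive. But it does not settle the matter. The same section also has non-target lesions assessed over time for progression, so an investigator could reasonably say that a 1.2 cm node can be followed. What remains is an ambiguity, not an express permission.

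Three further points stand:

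- The group is narrow. It needs a separate index lesion and no other non-irradiated disease that qualifies as a target.
- These patients can still be scored CR, so treating them as unscorable in Step 3 is a simplification. Zero responses in 20 enrolled patients remains a valid statement about the scored response rate in those enrolled.
- Section 8.0 offers its cohort figures as examples and fixes no response analysis set, so it is an inference that these patients stay in the denominator.

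**Conclusion.** The mismatch for nodes is real, and neither Section 5.8 nor Section 8.0 repairs it. Its reach is limited to metastatic patients with node-only non-index disease below the target limit, and to the secondary response rate. The primary endpoint, based on dose-limiting toxicity, is unaffected.

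A reader might go on to infer that the response rates are biased downward or that the zero-response statements are wrong. The documents do not support this. The statements reproduce as written, no count of affected patients is given, and there may be none. The shifted bounds show only how little slack there is: one unscorable patient would be enough for three of the four statements. They assume one-sided 95% bounds, removal of the affected patients from n, and no CR among them. The point is a cheap improvement to the wording, not a flaw that undermines the design.

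**What to change.** Keep the opening of criterion 10, "Patients who have metastatic cancer must have at least one lesion that is outside the radiation field", and follow it with: and that is a measurable target lesion as defined in Section 7.1.4.4.2 (extranodal at least 1.0 cm longest diameter, or nodal at least 1.5 cm short axis). Leave the existing 10% dose sentence as it is.

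The restriction to metastatic patients must stay. Criterion 5 admits "Locally advanced or metastatic pancreatic cancer for the pancreatic cancer cohort", and without the restriction the new wording would bar locally advanced patients who have no second lesion. Because criterion 10 does not reach those patients, a short definition of the response-evaluable set in Section 8.0 would be a useful companion. It would say how patients without a non-irradiated target lesion are counted.

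The change is one sentence and uses the baseline imaging already scheduled in Section 6.0, so it adds no procedure. Its cost is that a few patients with only small nodal disease outside the field are not enrolled.

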3.2 Secondary Objectives

Objective: To estimate the immune-related response rate in non-index metastatic lesions of the combination of Pembrolizumab and hypofractionated radiotherapy

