4.0 BACKGROUND & RATIONALE

4.1 Background

Historically patients with metastatic disease from epithelial cancers have rarely been cured. The 5-year survival rates for patients diagnosed between 2004 and 2010 with

metastatic NSCLC, melanoma, and breast cancer are respectively 4%, 16%, and 25% (<http://seer.cancer.gov/statfacts/>). Pancreatic cancer, regardless of stage has a poor prognosis, with an overall survival rate of 6.7%. For patients with localized pancreatic cancer, survival is 25.8%, with regional disease 9.9% and with distant metastases 2.3%.

Hypofractionated radiotherapy for oligometastatic disease

Hypofractionated radiotherapy for metastatic disease is commonly delivered with stereotactic body radiotherapy (SBRT) in which several non-coplanar photon beams are used to treat a tumor with a high degree of conformality resulting in little dose to surrounding normal tissues. SBRT has proven to be an effective local treatment for small, localized tumors. Initially, it was integrated as an ablative approach with a goal of tumor sterilization in oligometastatic disease with minimal morbidity and good long-term clinical outcome in these highly selected patients (1-4). Our goal in this protocol is different; we propose to use hypofractionated radiotherapy, either with or without an SBRT technique, to irradiate a single lesion in the setting of immune checkpoint blockade with the hope of augmenting a systemic response.

Immunologic approaches to treating patients with advanced stage cancer

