The following are examples of response rates and exact 95% CIs based on 38 patients in Cohort 1 and 32 patients in Cohort 2.

Table 14

Cohort 1			Cohort 2		
N= 38 patients			N = 32 patients		
# Respond	Response Rate	95% exact CI	# Respond	Response Rate	95% exact CI
5	13.2%	4.4 – 28.1%	4	12.5%	3.5 – 29.0
10	26.3%	13.4 – 43.1%	8	25.0%	11.5 – 43.4
19	50.0%	33.4 – 66.6%	16	50.0%	31.9 – 68.1
30	78.9%	62.7 – 90.4%	24	75.0%	56.6 – 88.5
35	92.1%	78.6 – 98.3%	28	87.5%	71.0 – 96.5

Next we will evaluate response rate by disease site. Here we pool fractionation cohorts. This is an assessment of RADVAX™ activity by disease, although preliminary.

Table 15

Disease	Safety Phase (Number is expected not required**)	Expansion Phase (Number is required)	STUDY TOTAL
Melanoma	6	14	20
NSCLC	6	14	20
Pancreas	4	6	10
Breast	4	6	10
Other cancers	4	6	10

** assumes equal numbers by disease strata in (12 prior PD-1 and 12 no prior PD-1)

For Melanoma and NSCLC cohorts: If 0/14 in the expansion phase respond then we can rule out a 20% response rate with 95% confidence. If 0/20 (pooling both phases) respond, then we can rule out a 15% response rate with 95% confidence.

For Pancreas, breast cancer and other cancers: If 0/6 in the expansion phase respond then we can rule out a 40% response rate with 95% confidence. If 0/10 (pooling both phases) respond, then we can rule out a 27% response rate with 95% confidence.

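### The 10% dose limit covers only the one lesion needed for eligibility, so a lesion close to the index lesion that receives more than that can still count towards the non-index response

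*Combined protocol and SAP*

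**What the plan says.** The secondary objective in section 3.2 is "To estimate the immune-related response rate in non-index metastatic lesions".

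Section 5.1.2, criterion 10, says that patients with metastatic cancer "must have at least one lesion that is outside the radiation field", larger than one centimetre and followable by RECIST 1.1. It then adds a dose condition: "This lesion, if it is close to the radiated lesion, must receive no more than 10% of the dose prescribed to the target lesion". Both sentences are in the singular and concern the lesion that makes the patient eligible.

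Section 7.1.4.4.2 governs scoring: "A maximum of 5 target lesions in total (and up to 2 per organ) can be identified at baseline". Its only exclusion related to radiation is: "The irradiated lesion will not be included as a target lesion for measurement using RECIST". Partial response is a fall of 30% or more in the summed diameters.

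Elsewhere the irradiated lesion means one lesion. Section 4.1 states the aim as to "irradiate a single lesion in the setting of immune checkpoint blockade", and section 4.2, describing the group's ipilimumab trial, treats irradiated and index as the same thing.

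Section 8.0 gives "examples of response rates and exact 95% CIs based on 38 patients in Cohort 1 and 32 patients in Cohort 2", together with the response rate that zero responders would rule out in each disease group.

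**The concern.** The protocol accepts that a lesion above 10% of the prescribed dose is not a clean witness to a systemic effect, and applies this to the eligibility lesion. It does not apply it to the other lesions that decide response. The eligibility lesion need not even be among the target lesions. No text asks for the dose to each target lesion to be recorded, and section 8.0 has no analysis that sets aside lesions that received dose.

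The index site may be lung, liver, bone or soft tissue, and two target lesions per organ are allowed, so a same-organ neighbour can be in the sum. If it shrinks because it was partly irradiated, the patient may be scored as a responder with no change outside the field. What is at stake is the meaning of the non-index response rate, in disease groups small enough for one patient to matter.

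**Working it through.** **1. The two rules side by side.**
- Dose limit (5.1.2, criterion 10): at least one lesion, the qualifying one. For 8 Gy x 3 it is 0.10 x 24 = 2.4 Gy; for 17 Gy x 1 it is 0.10 x 17 = 1.7 Gy.
- Lesions summed (7.1.4.4.2): up to five, up to two per organ.
- Lesions removed from the sum: the irradiated lesion, singular.

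A lesion that is neither the index lesion nor the qualifying lesion therefore has no dose condition.

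**2. The plan's own figures.** The exact (Clopper-Pearson) two-sided 95% intervals reproduce all ten rows of Table 14, for example 5/38 = 13.2% (4.4 to 28.1%) and 4/32 = 12.5% (3.5 to 29.0%). The zero-response rules follow from the one-sided 95% upper limit 1 - 0.05^(1/n):
- 0/14: 19.3% (plan: 20%)
- 0/20: 13.9% (plan: 15%)
- 0/6: 39.3% (plan: 40%)
- 0/10: 25.9% (plan: 27%)

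All stated rules hold, and none changes with the fix.

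**3. Can near-field shrinkage alone give a partial response?** Assume m target lesions of equal diameter, k of them near the field, and the rest unchanged. A 30% fall in the sum needs each near-field lesion to shrink by s = 0.30 x m / k.

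| Target lesions m | Near-field k | Shrinkage needed |
|---|---|---|
| 1 | 1 | 30% |
| 2 | 1 | 60% |
| 3 | 1 | 90% |
| 4 | 1 | 120%, impossible |
| 5 | 1 | 150%, impossible |
| 3 | 2 | 45% |
| 4 | 2 | 60% |
| 5 | 2 | 75% |

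Unequal sizes shift these figures. With assumed sizes, a compliant 2.0 cm lesion that does not change and a near-field 3.0 cm lesion that falls to 1.5 cm take the sum from 5.0 to 3.5 cm: 1.5 / 5.0 = 30%, a partial response.

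**4. The opposite case.** If the compliant lesion falls from 2.0 to 1.4 cm, it alone shows a 30% fall. Add an unchanged 3.0 cm neighbour and the sum goes from 5.0 to 4.4 cm: 0.6 / 5.0 = 12%, not a partial response.

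**5. Effect of false responders.** Their number is an assumption: one, or two in the fractionation cohorts. Intervals are two-sided exact 95%.
- Disease groups, expansion phase: 0/14 becomes 1/14 = 7.1% (0.2 to 33.9%); 0/6 becomes 1/6 = 16.7% (0.4 to 64.1%). The one-sided upper limit rises from 19.3% to about 29.7%, and from 39.3% to about 58.2%.
- Disease groups, both phases: 0/20 becomes 1/20 = 5.0% (0.1 to 24.9%); 0/10 becomes 1/10 = 10.0% (0.3 to 44.5%).
- Cohort 1: 5/38 becomes 6/38 = 15.8% (6.0 to 31.3%) or 7/38 = 18.4% (7.7 to 34.3%).
- Cohort 2: 4/32 becomes 5/32 = 15.6% (5.3 to 32.8%) or 6/32 = 18.8% (7.2 to 36.4%).

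**The case against.** The best defence is the exclusion sentence itself. In ordinary usage a neighbour that takes a substantial share of the dose is an irradiated lesion, so 7.1.4.4.2 may already remove it. That reading is possible, but the wording is singular and the protocol uses the term for the index lesion. Even on the broad reading, a lesion outside the field that receives more than 10% stays in the sum.

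The second defence is that the situation should be uncommon. Section 5.2 asks for highly conformal dose distributions and, for SBRT, no aperture margin beyond the planning volume; section 4.2 speaks of an isolated index lesion. This stands as a point about frequency, but these passages do not govern which lesions are scored. Nor will every patient have SBRT, and the minimum field dimension of 3.5 cm can extend past the planning volume when the index lesion is small. Criterion 10 itself foresees lesions close to the irradiated one.

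Two stronger readings do not hold:
- A reader might infer that the error always favours the treatment. Step 4 of the working shows that a near-field lesion that does not shrink can hide a real response, and its growth would count towards progression.
- A reader might infer that the two regimens are biased differently. The documents give one set of planning rules for both, and show neither a difference in relative dose spill nor a direction.

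**Conclusion.** The gap is real: a target lesion other than the index lesion can exceed the protocol's own dose limit and still contribute to the non-index response. The effect is largest with one to three target lesions or with two near-field lesions; for equal lesions with the others unchanged, one of four or five cannot give a partial response alone. One false responder is enough to take a disease group out of its zero-response rule (0/14 to 7.1%, 0/6 to 16.7%).

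The size rests on assumptions: equal diameters, other lesions unchanged, and one or two affected patients. The documents give no dose to neighbouring lesions and no basis for how often this would occur. Only a descriptive secondary estimate is affected. The dose-limiting-toxicity endpoint, the sample size and the stated confidence limits stand. It is still worth correcting, because the contamination goes to what the estimate means and the remedy is cheap.

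**What to change.** In 7.1.4.4.2, replace the exclusion sentence with wording such as: *The index lesion, and any other lesion receiving more than 10% of the prescribed dose on the approved radiotherapy plan, may not be a target lesion for the non-index response.* Check this on the existing plan when target lesions are listed, and record the dose to each. State whether lesions excluded in this way are followed as non-target lesions, since complete response requires all known lesions to disappear. Align the terms as well: criterion 10 calls the irradiated lesion the target lesion, whereas 7.1.4.4.2 says it is never one.

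For patients already enrolled, report a sensitivity analysis of response that leaves out target lesions above the limit.

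The cost is one sentence and a look at plans already made; no treatment, sample size or interval changes. Some patients will have fewer target lesions. Criterion 10 does not by itself guarantee that one remains: it accepts a lesion larger than one centimetre, while 7.1.4.4.2 requires 1.5 cm in short axis for a nodal target. The qualifying lesion should therefore also be required to meet the measurable size in 7.1.4.4.2.
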